8 DESCRIPTION OF THE DEVICES

All components of the Scorpio systems used in this study obtained the CE mark and have been approved for sale and use throughout Europe. The devices are described in the product information (appendix 4 and 5).

9 PATIENT EVALUATIONS

Patients will be assessed pre-operatively, per-operatively and post-operatively. Appropriate data will be recorded both in their hospital notes and case report forms. The follow-up intervals are described in the following table.

Table 2: follow up intervals

Evaluation	Pre-op	Per-op	Post-operatively						
			Prior to Discharge	6 wks	12 wks	26 wks	1 Year	2 Years	5 Years
Medical History	√								
Clinical + KSS	√			√	√	√	√	√	√
Operative Data		√							
Chair Raise test Stair climb test	√			√	√	√	√	√	√
X-rays A/P en lateral	√		√	√	√	√	√	√	√
X-rays Long leg	√				√				
X-rays Patella defile	√				√	√	√	√	√
WOMAC, EQ-5D Patient evaluation	√				√	√	√	√	√

9.1 Evaluations at each assessment

9.1.1 Pre-operative Evaluation

- Clinical History(*clinical researcher*)

- Date informed consent obtained
- Patient initials, study number
- Date of birth, weight, height, and gender
- Knee for surgery
- Primary diagnosis
- Previous knee surgery

- Clinical Evaluation(*physiotherapist*)

- Knee Society Score Evaluation
 - Pain
 - Walking
 - Stairs
 - Support
 - Flexion Contracture
 - Extension Lag
 - Range of Motion (active / passive)
- Stability-Anteroposterior
- Mediolateral stability
- Patella tracking
- Chair raise test and stair climb test
- WOMAC, EQ-5D patient evaluation questionnaires

- Radiographic Evaluation(*clinical researcher*)

- Date of graphs taken
- Leg axis
- Femoral tibial angle
- Patella tilting

9.1.2 Intra-operative Evaluation

- Surgical details(*surgeon*)

- Date of surgery
- Scorpio implant and component fixation
- Surgical approach
- Type of anaesthesia

- Anaesthesia class
- Systemic prophylactic therapy
- Gaps
- Implant sizes
- Valgus angle
- Passive range of motion
- Computer navigation details

9.1.3 At Discharge(clinical researcher)

- Date of discharge
- Mobilisation figures (date out of bed and date mobilisation)
- Complications
- Active Range of Motion
- X-graph post-op evaluation

9.1.4 Post-operative Evaluation

Patients will be assessed at post operative intervals at 6 weeks 3 months, 6 months 1, 2 and 5 years.

Post-operatively

- **Clinical Evaluation(*physiotherapist*)**
 - Date of assessment
 - Complications
 - Knee Society Score Evaluation
 - Pain
 - Walking
 - Stairs
 - Support
 - Flexion Contracture
 - Extension Lag
 - Range of Motion (active and passive)
 - Stability-anterposterior
 - Mediolateral stability
 - Patella tracking
 - Chair raise test, stair climb test
 - WOMAC, EQ-5D patient evaluation questionnaires

- **Radiographic Evaluation(*clinical researcher*)**

- Date of graphs taken
- AP and Lateral view
- Radiolucencies
- Patella tilt

9.2 *Adverse event/ Complications (surgeon)*

- Intra-operative and post-operative complications
- Date of event/complication
- Local complications
- Mechanical complications
- Revision required
- General complications
- Outcome complication

10 ADVERSE EVENTS

The investigator is required to document in the adverse event/complication section of the CRF all operative site and general medical complications, including date of occurrence, date diagnosed, type of complication and treatment.

10.1 *Definitions*⁶

An **adverse event** is “any untoward medical occurrence in a subject (this definition does not imply that there is a relationship between the adverse event and the device under investigation)”.

A **serious adverse event** is an adverse event which

- a) led to a death
- b) led to a serious deterioration in the health of a subject that
 1. resulted in a life-threatening illness or injury,
 2. resulted in a permanent impairment of a body structure or a body function,
 3. required in-patient hospitalization or prolongation of existing hospitalisation,
 4. resulted in medical or surgical intervention to prevent permanent impairment to body structure or a body function.
- c) led to foetal distress, foetal death or a congenital abnormality or birth defect.

An **adverse device effect** is “any untoward and unintended response to a medical device (this definition includes any event resulting from insufficiencies or inadequacies in the instructions for use or the deployment of the device. This definition includes any event that is a result of a user error)”.

A **serious adverse device effect** is “an adverse device effect that has resulted in any of the consequences characteristic of a serious adverse event or that might have led to any of these consequences if suitable action had not been taken or intervention had not been made or if circumstances had been less opportune”.

All **serious adverse device effects** must be reported to Stryker by telephone, or in writing, ideally within 24 hours after the investigator first learns of the event. This can be either to the Surveillance project manager (details mentioned on page 10) or the local country product manager. The investigator also has to inform his Ethics Committee about any **serious adverse device effects**.

11 PATIENT WITHDRAWALS

Every attempt must be made to ensure that all the patients return for all of the post-operative assessments. However, patients are free to withdraw from the Investigation at any time and are under no obligation to provide a reason for doing so. Patients who withdraw from the Investigation should have the reason for their withdrawal recorded on the case report forms (CRF's), if at all possible. All attempts should be made to ascertain whether any patient apparently lost to follow up has actually chosen not to return or is deceased.

12 REPORTING OF RESULTS

All the above-mentioned pre-operative patient assessments, per-operative details and post-operative follow-up assessments will be recorded on the CRFs (Case Record Forms), which will be provided, and also in a database.

A case record form will be completed for each patient.

All data recorded in the CRFs should be in agreement with the information reported in the patient's hospital records and other primary sources of data.

In order to maintain patient confidentiality, the patient's name or address will not be recorded on the form. Only the patient's study number will be recorded on the CRF. For means of tracing the patient the scientific researcher has a code list on which patient study number and his name, date of birth and patient hospital number is mentioned.

These case record forms must be completed, checked for accuracy and signed by the investigator.

13 INVESTIGATION MONITORING

During the course of the Surveillance and thereafter until the centre has been closed, the monitor(s) possibly visit the Surveillance centre(s) by prior arrangement. The clinical Surveillance project manager or Surveillance monitor can also be contacted concerning any problems or queries regarding the clinical Surveillance.

CRA: [name]
Clinical Research Associate
[contact] (direct)
E-Mail: [contact]

Upon completion of the CRF, the Monitor will send a copy of the CRF to Stryker Data Management for data entry.

The monitor shall be given unhindered access to Surveillance relevant source documents (including medical records) to enable complete data verification, but with respect to the patient's integrity as described in section 17.4.

14 ANALYSIS OF RESULTS

Results obtained from the Surveillance will be tabulated and statistically analysed by Stryker's Clinical Research Department using an appropriate statistical software package.

14.1 Statistical Analysis

There will be summaries and comparisons presented according to:

- Demographic and pre-operative assessments
- Operative assessments
- Post-operative pain and function assessments
- Chair raise and stair climb assessment
- Patella-tracking assessment
- Adverse events
- General complications
- Local complications
- Device-related complications
- Revisions/removals

Descriptive statistics will be used like frequency and percent distributions and will be presented in tabular form for categorical variables. The mean, standard deviation, minimum and maximum values will be presented for quantitative variables. Students T-test will be used to compare variables between groups and various time points.

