3 OBJECTIVES

The primary objective is to compare the maximum flexion, both passive and active at every clinical follow-up time point up till 5 years postoperative, measured with a large goniometer. Our primary hypothesis is that the Scorpio NRG PS knee prosthesis has an average flexion of at least 7 degrees higher than the Scorpio PS knee prosthesis. Secondary objectives are to assess the complications, Chair raise test outcomes, knee pain (VAS) and surgery time. The secondary hypothesis is that there is no difference in complications and pain during the stair climb and chair raise test between the Scorpio NRG PS and the Scorpio PS. So more flexion does not result in more anterior knee pain. Also, the validity of computer navigated measurements and the relation between patella tilting and post-operative pain will be evaluated.

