4 METHODS

Performance will be clinically measured using the Knee Society Score (Ewald, 1989; appendix 2). As part of the KSS flexion will be measured, both passive and active. The measurement will be done by a physiotherapist. Like the patient the physiotherapist will be blinded for the treatment.

The Chair Raise test(standing up from a firm straight-backed chair keeping the arms folded across the chest) and stair climb test(ascending a flight of eleven 17.8 cm tall steps with an 30 cm tread depth, use of one hand rail is allowed) is combined with a 10 point VAS measurement of anterior knee pain(McCormack et al., 1988). This consists of a pain scale from 0 to 10 on which the patient can point to the amount of pain (0 means no pain, 10 means the worst possible pain) Recording of the nature and incidence of all intra-operative and post-operative complications will be the method to assess safety. The difference between computer navigation measurements of leg axis and range of motion and clinical and X-ray measurements of these parameters will be evaluated. For this evaluation the pre-op standard X-rays and the per-operative computer navigation data will be used.

The relation between patella tilting and post-operative pain will be measured during functional tests Stair climb and chair raise according to a Visual analog scale (VAS) .

Patellar tilting will also be assessed on consecutive X-rays by the orthopaedic surgeon.

A WOMAC patient questionnaire (appendix 3) will be done to evaluate the patient's opinion on recovery, post-operative pain, and function(Bellamy et al., 1988).

An EQ-5D patient questionnaire (appendix 3) will be done to evaluate the patient's opinion of their health status (mobility, self-care, usual activities, pain/discomfort, anxiety/depression and a visual analog scale (VAS) to measure the patient's self-rated health outcome).

All evaluations will be conducted on the follow up moments mentioned in the follow up table

at page 8.

The prostheses used in this study both have a CE mark. All information concerning these prostheses is attached as appendix 4

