6 SELECTION OF PATIENTS

6.1 *Number of patients*

The number of patients is based on average postoperative flexion as the primary endpoint. According to Morawa¹⁰ Scorpio patients showed a maximum post-operative flexion of 104 degrees. An increase in maximum flexion of 5 degrees is already noticeable for the patient, so clinically important. According to pre marketing results the Scorpio NRG PS knee prosthesis can reach a flexion of more than ten degrees extra compared to the Scorpio PS. For the primary endpoint we want to aim at an increase in maximum flexion of 7 degrees. According to Schouten¹² a sample size of 40 patients in each group is needed with a difference in flexion of 7 degrees, a standard deviation of 11^{7,8} a 80% power with a significance level (alpha) of 0.05 (two-tailed). When we take into account a lost of FU of 10% a total groupsize of 88 is anticipated.

6.2 *Patient selection criteria*

All patients on the waiting list for a total knee prosthesis at the department of orthopaedics at the AZM will be checked for suitability for this study. Patients will be verbally and in writing informed about the study during the first visit related to the TKP, and will be provided with the patient information. One week before surgery during a pre-operative visit the patients will be orally informed again, All questions about the study will be answered and the patient will be asked to participate in this study. If a completely informed patient wants to participate, the informed consent will be signed.

If a patient doesn't want to participate it is very likely that he will receive the Scorpio PS prosthesis since this is the standard used knee prosthesis at the AZM. If a patient does or doesn't want to participate has no effect on day of surgery or further medical care.

The confidentiality of the subject will be maintained at all times. The patient will be told that he/she is free to refuse the collection of his/her clinical data or to withdraw from the Investigation at any time without compromising future medical care.

TABLE 1. Patient Inclusion and Exclusion Criteria

Inclusions

- Patients requiring a primary TKA
- Male and nonpregnant female patients
- Between 18 and 80 years of age at time of surgery
- Patients with a diagnosis of osteoarthritis (OA), avascular necrosis (AVN), and not severe posttraumatic arthritis
- No previous osteosynthesis of the involved knee during the last 12 months

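### Flexion is compared with an unadjusted t-test although every patient's pre-operative flexion is recorded; adjusting for it would gain precision at almost no cost

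*Combined protocol and SAP*

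**What the plan says.** The statistical method is confined to Section 14.1: descriptive summaries, followed by "Students T-test will be used to compare variables between groups and various time points". No covariate, ANCOVA, regression or repeated-measures model is mentioned. Section 14 adds only that suitable software will be used.

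Flexion is the primary outcome. Section 3 sets out to "compare the maximum flexion, both passive and active at every clinical follow-up time point", up to 5 years. Section 6.1 plans the trial on an unadjusted comparison: "a sample size of 40 patients in each group is needed with a difference in flexion of 7 degrees", with a standard deviation of 11, 80% power and a two-sided alpha of 0.05.

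The same measurement is taken before surgery. Section 4 states: "As part of the KSS flexion will be measured, both passive and active". Table 2 in Section 9 schedules the clinical and Knee Society Score (KSS) evaluation pre-operatively, Section 9.1.1 lists "Range of Motion (active / passive)" among the pre-operative items, and Section 2.1 has the pre-operative assessments completed once consent is signed.

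**The concern.** A baseline measurement of the primary outcome is often its strongest single predictor, and here it is collected before the implant can affect it. An analysis that ignores it leaves in the residual variance whatever part of post-operative flexion the pre-operative value explains. The confidence interval is then wider than it needs to be for the same patients.

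By chance the two groups may also differ in mean pre-operative flexion. If the pre- and post-operative standard deviations are equal, r times that difference stays in the unadjusted estimate. The t-test's standard error already allows for this, so it is not a bias, but adjustment would remove it.

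Precision matters here because Section 6.1 regards 5 degrees as noticeable to the patient and clinically important, and the planned analysis has a half-width of almost that size. There is also little reserve: power is only just 80%, the allowance for loss over 5 years is 10%, and Section 2.2 removes some patients during surgery.

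**Working it through.** **Inputs from the documents (Section 6.1):** difference 7 degrees, SD 11, 40 per group, two-sided alpha 0.05, power 80%, 10% loss, total 88.

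**Assumed input:** the pre/post correlation r. The documents give none, so a range of 0.2 to 0.6 is shown, with r = 0 as the worst case.

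**1. The plan's own figure.**
- Normal approximation: n per group = 2 × [11 × (1.960 + 0.842) / 7]² = 38.8, so 39.
- With the t distribution: 39.75, so 40, as stated.
- Loss to follow-up: 80 × 1.10 = 88, as stated. (Dividing instead, 80 / 0.90 gives 89.)

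**2. The planned t-test, 40 per group.**
- SE = 11 × √(2/40) = 2.46 degrees.
- Half-width of the 95% interval = 1.991 × 2.46 = 4.90 degrees (78 degrees of freedom).
- Power for 7 degrees = 80.3%.

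**3. ANCOVA with pre-operative flexion as covariate.**
- Residual SD = 11 × √(1 − r²).
- Estimating the slope costs one degree of freedom (77 left) and multiplies the variance of the difference by about 1 + 1/76.
- SE = residual SD × √[(2/40) × (1 + 1/76)].
- Example, r = 0.5: residual SD = 11 × √0.75 = 9.53; SE = 9.53 × √(0.05 × 1.0132) = 2.14; half-width = 1.991 × 2.14 = 4.27.

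| Analysis | r (assumed) | Residual SD | Half-width (degrees) | Power for 7 degrees |
|---|---|---|---|---|
| t-test | any | 11.00 | 4.90 | 80.3% |
| ANCOVA | 0 | 11.00 | 4.93 | 79.7% |
| ANCOVA | 0.2 | 10.78 | 4.83 | 81.3% |
| ANCOVA | 0.3 | 10.49 | 4.70 | 83.3% |
| ANCOVA | 0.4 | 10.08 | 4.52 | 86.1% |
| ANCOVA | 0.5 | 9.53 | 4.27 | 89.7% |
| ANCOVA | 0.6 | 8.80 | 3.94 | 93.7% |

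Leaving out the small ANCOVA penalty raises these powers by at most about half a point. All figures are for one comparison: one flexion type at one visit.

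**4. Break-even.** The standard error improves once (1 − r²) × (1 + 1/76) is below 1, that is r² above 1/77, or r above about 0.11.

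**5. Simulation.** With 40,000 simulated trials for each of r = 0, 0.2, 0.3, 0.5 and 0.6, type I error was 4.8 to 5.1% for the t-test and 4.7 to 5.1% for ANCOVA. ANCOVA power was 81.2%, 83.6%, 89.5% and 93.6% for r = 0.2, 0.3, 0.5 and 0.6, in line with the table.

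**6. Two consequences.**
- For a true difference of 5 degrees, the t-test has 52% power and ANCOVA at r = 0.5 has 63%.
- If only 36 per group were analysed (an illustration), the t-test would have 76% power for 7 degrees and ANCOVA at r = 0.4 would have 82%.

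**7. Change scores are not a substitute.** With equal SDs, the SD of the change is 11 × √[2(1 − r)]: 13.02 at r = 0.3 and 11.00 at r = 0.5. Below r = 0.5, a t-test on change is less precise than one on the post-operative value.

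**The case against.** The strongest reply is that the plan contains no error. The t-test is valid, it matches the unadjusted sample size calculation, and the trial reaches its own power target with it. That is right, and it is why this is a recommended improvement rather than a defect that must be corrected.

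Secondly, the benefit rests on a correlation the documents do not supply. That also stands. That pre-operative flexion predicts post-operative flexion is an assumption here, and r may differ by visit from 6 weeks to 5 years and between active and passive flexion. At r = 0.2 the gain is only 1.0 point of power and 0.07 degrees of half-width. But the risk is lopsided: about half a point of power lost if r = 0, against 13.4 points gained at r = 0.6.

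Thirdly, Section 14.1 lists pre-operative assessments among its comparisons and Section 2.3 speaks of improvement in the KSS, so baseline might yet be used. Neither passage describes a baseline-adjusted comparison of the groups, and the most that could be read into them is a change score.

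Finally, adjustment does not settle the multiplicity of two flexion types at six post-operative visits. That is true, and it is a separate matter.

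**Conclusion.** The concern holds as a matter of efficiency. Section 14.1 leaves unused a baseline measurement that the trial already collects. The planned test is valid and unbiased, and the sample size stands.

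For a single comparison with 40 per group and SD 11, adjustment adds between 1.0 point of power (r = 0.2) and 13.4 points (r = 0.6), and shortens the confidence interval half-width by 0.07 to 0.96 degrees. It is worth having from about r = 0.4, where power is 86.1%. That no covariate is specified is certain; the size of the gain is conditional on the assumed r and on a linear relation with similar residual variance in both groups. The change should be made, and made before any outcome data are examined, because a choice to adjust taken after seeing results invites selective reporting.

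**What to change.** In Section 14.1, state that each between-group comparison of flexion includes pre-operative flexion of the same type as a covariate (active for active, passive for passive), and that the adjusted difference is reported with its 95% confidence interval.

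Section 3 covers every follow-up visit and names no primary one, so specify in advance one of:
- ANCOVA at each visit; or
- for each flexion type, one repeated-measures model with treatment, visit, treatment-by-visit interaction and baseline flexion, which is valid if data are missing at random.

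The first is enough for the point made here. Keep the unadjusted t-test as a sensitivity analysis.

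The cost is a few sentences in Section 14.1 and slightly more analysis work. The sample size, visit schedule and case report form do not change.

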7 LENGTH OF SURVEILLANCE

The study has a follow up of 5 years. An inclusion period of 1,5 years is anticipated, so the study will run for 1,5 plus 5 years. When the inclusions start in June 2010, the study will end March 2016. The table below gives us an overview of the time window per visit.

VISIT	TIME WINDOW
Pre-op.	Date of or any time post the date of written informed consent up to the date of surgery.
Operation	N/A
PTD	N/A
6 weeks post-op.	± 1 week
12 weeks post-op	± 2 weeks
26 weeks post-op	± 2 weeks
1 year post-op	± 2 months
2 year post-op	± 2 months
5 years post-op	± 2 months

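### A t-test at a late visit ignores the earlier flexion of patients lost by then; a repeated-measures model on data already collected would limit possible, though not certain, bias

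*Combined protocol and SAP*

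**What the plan says.** Section 3 (Objectives) states the primary aim as to "compare the maximum flexion, both passive and active at every clinical follow-up time point up till 5 years postoperative". Table 2 in section 9 gives six such visits: 6, 12 and 26 weeks, and 1, 2 and 5 years.

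Section 14.1 is the whole analysis plan. Besides descriptive summaries it says only: "Students T-test will be used to compare variables between groups and various time points". It names no repeated-measures model, missing-data rule or sensitivity analysis.

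Loss to follow-up appears in two other places. Section 6.1 enlarges the sample: "When we take into account a lost of FU of 10% a total groupsize of 88 is anticipated". Section 11 (Patient withdrawals) asks for efforts to bring patients back, for reasons to be recorded where possible, and for checks on whether those apparently lost declined to return or died. Nothing from section 11 is carried into the analysis.

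**The concern.** A two-sample t-test of flexion at 5 years can use only patients measured at 5 years. Someone seen at all five earlier visits who then stops attending adds nothing to that comparison, although the earlier readings say a good deal about where the knee was heading. That patient still counts in the comparisons at the visits attended, so the gap concerns late visits. Section 14.1 does not say in so many words that testing is visit by visit; this is the natural reading of it together with section 3.

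Extra recruitment restores the count but not the comparability of those who remain. If patients with stiffer knees stop attending more often, and more so in one arm, the attenders' difference moves away from the true one. There is no visit between 2 and 5 years, and section 15 plans a separate 5-year paper, so the most exposed comparison is one that will be published.

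**Working it through.** **Inputs from the documents.** Section 6.1: "a sample size of 40 patients in each group is needed with a difference in flexion of 7 degrees", "a standard deviation of 11", 80% power, two-sided alpha 0.05, and 88 patients in total, taken as 44 per arm. Section 7: "The study has a follow up of 5 years".

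**Inputs assumed.** The documents give no loss rate by arm, no correlation between visits and no link between loss and flexion. All three are assumptions below and are varied.

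**1. The plan's own figure.** n per arm = 2(1.960 + 0.842)² × 11² / 7² = 38.8, so 39. The t-based calculation gives 39.7, so 40, as stated. Then 80 × 1.10 = 88, as stated.

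**2. What the 10% covers.** For attenders, SE = 11 × √(2/m), with m = 44 × (1 − loss). Power uses the normal approximation.

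| Loss | m per arm | SE | 95% CI half-width | Power, t-test | Power using earlier visits, correlation 0.5-0.8 |
|---|---|---|---|---|---|
| 10% | 39.6 | 2.47 | 4.85 | 80.8% | 81.8-83.3% |
| 20% | 35.2 | 2.62 | 5.14 | 76.1% | 78.2-81.6% |
| 30% | 30.8 | 2.80 | 5.49 | 70.4% | 73.8-79.3% |

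If loss is random, the allowance does its job up to 10%.

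**3. Precision gain under random loss.** Let r be the correlation between the earlier and late reading, n = 44 randomised and m attending per arm. The variance relative to the attenders' t-test is m × [(1 − r²)/m + r²/n].

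- m = 40, r = 0.6: 0.64 + 0.36 × 40/44 = 0.967. With r = 0.8: 0.36 + 0.64 × 40/44 = 0.942. The gain is 3-6%.
- m = 35, r = 0.6: 0.64 + 0.36 × 35/44 = 0.926. With r = 0.8: 0.36 + 0.64 × 35/44 = 0.869. The gain is 7-13%.

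**4. Bias under loss that depends on flexion.** Flexion at 2 and 5 years was simulated with 44 per arm, SD 11 and a true difference of 7 degrees. Patients were picked for loss with weight exp(−k·z), where z is 2-year flexion in SD units within the arm. With k = 1.5 (steep), a patient 1 SD below the mean is e³, about 20, times as likely to be picked as one 1 SD above. With k = 0.5 (mild) the ratio is e¹, about 2.7.

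| Loss, control v NRG | Selection | Mean attenders' difference, by correlation | Shrinkage |
|---|---|---|---|
| 15% v 5% | steep | 6.1, 5.9, 5.8 (0.6, 0.7, 0.8) | 0.9-1.2 |
| 25% v 10% | steep | 5.7, 5.6, 5.3 (0.6, 0.7, 0.8) | 1.3-1.7 |
| 15% v 5% | mild | 6.7, 6.5 (0.6, 0.8) | 0.3-0.5 |
| 25% v 10% | mild | 6.4, 6.2 (0.6, 0.8) | 0.6-0.8 |
| equal rate, same selection | either | 7.0 | none |

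Repeat runs agree to about 0.1 degree, apart from small differences in how fractional losses are rounded. They put the largest mild shift nearer 0.7 and the largest steep shift at 1.6-1.7. The likelihood estimate that uses the 2-year value averages 7.0 throughout.

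**5. Consequence for power.** At 15% v 5% the total loss is exactly the planned 10%. SE = 11 × √(1/37.4 + 1/41.8) = 2.48. With an expected difference of 5.8-6.1 (steep selection), power is about 65-70%, against the planned 80%.

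**The case against.** The best opposing case is that differential loss is conjecture. Patients and the assessing physiotherapist are blinded, both arms have the same visits, and nothing in the documents points to a threefold difference in loss. The larger shifts need steep selection as well as unequal loss. Even 1.7 degrees is well inside a 95% CI half-width of 4.85 degrees. This stands as a limit on size, and it rules out calling the bias large without qualification.

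Blinding does not remove the possibility, however. Suppose one rule applies in both arms: the lower the absolute flexion, the likelier the loss. If NRG knees flex further, fewer of them are stiff, and loss then differs by arm. With an assumed logistic slope of 1.5 per SD and 10% lost overall, loss is 13% v 7% and the attenders' difference is 6.4-6.5 degrees; with a slope of 1.0 it is 6.6-6.7.

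Two further objections hold. First, the precision gain in step 3 belongs to random loss, where there is no bias. Where loss is selective the gain is small: at 15% v 5% with steep selection, the SD of the estimate was 2.47 by either method at correlation 0.6, and 2.43 v 2.37 at 0.8. Second, the model recovers 7.0 because loss was simulated from observed 2-year flexion. A knee that stiffens after 2 years and then goes unseen is not covered.

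A reader might infer that lost patients are discarded altogether, or that the plan does nothing about loss beyond the 10%. The documents support neither: earlier readings enter the earlier comparisons, which section 3 counts as primary, and section 11 provides for retention and tracing.

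**Conclusion.** The point holds as a modest improvement to the analysis. At late visits the planned t-test leaves out relevant flexion already recorded, and nothing in the plan addresses bias from selective loss. Under the assumed loss rates, shrinkage of a true 7-degree difference is about 0.3-0.7 degrees with mild selection and 0.9-1.7 with steep selection. It is nil when rate and selection are the same in both arms. In these scenarios the shift is towards no difference; other patterns of loss could act differently.

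It would be tempting to conclude that the 5-year result will be biased or that the trial is underpowered. The documents do not support either. Bias depends on a loss pattern they do not describe, and the stated sample size reproduces and keeps about 80% power at 10% random loss.

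**What to change.** In section 14.1, analyse flexion with a mixed model for repeated measures on all six post-operative visits, with arm, visit and arm-by-visit as fixed effects and an unstructured covariance. Report the arm difference with 95% CI at each visit, and name one visit in advance as primary; the protocol currently names none.

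Beside it:

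- keep the attenders-only t-test as a secondary result;
- add a simple sensitivity analysis for loss not explained by observed flexion, for example a delta shift applied to the unobserved values;
- tabulate number lost and reason by arm and visit, using the reasons section 11 already asks for.

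The cost is SAP wording and slightly more analysis work; no new data are needed. The drawback is that the model assumes loss is explained by observed flexion, which is why the sensitivity analysis is needed. Patients with no post-operative reading still contribute nothing and should be counted in the table.
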